1. PROTOCOL SUMMARY

1.1 Schedule of Activities (SoA)

The procedures for the screening and treatment periods in this study are presented in

- [Table 1](#) for the dose-finding phase
- [Table 2](#) for the dose-expansion phase
- [Table 3](#) for the procedures for the follow-up period (for patients off study treatment).
- [Table 4](#) for the procedures (management, reporting) for patients receiving ongoing treatment beyond database cutoff

The timing of the vital signs assessments should be such that it allows the blood draw eg, pharmacokinetic (PK) blood sample, to occur at the timepoints indicated in the schedule of activities (SoAs). Whenever electrocardiograms (ECGs), vital signs, and blood draws are scheduled for the same nominal time, the assessments should occur in the following order: ECG, vital signs, and then blood draws. The timing of the first 2 assessments should be such that it allows the blood draw (eg, PK blood sample) to occur at the timepoints indicated in the SoAs. Vital signs should always be assessed before blood draws.

For both durvalumab monotherapy or durvalumab in combination with tremelimumab

- Patients may delay dosing under certain circumstances:
 - Dosing may be delayed per the Dosing Modification and Toxicity Management Guidelines, due to either immune or non-immune-related adverse events (AEs).
 - If dosing must be delayed for reasons other than treatment-related toxicity, dosing will resume as soon as feasible.
 - A treatment delay of up to 14 days is permitted in the event that any AEs prevent the patient from starting the following cycle as planned.

Table 1 Schedule of activities for durvalumab ± tremelimumab dose-finding phase

	Screening	Cycle 1 (28 days)			Cycle 2 (28 days)			Cycle 3 to progression (each cycle is 28 days)	End of Treatment visit	For details, see Section
Day of cycle	-28 to -1	1	8	15	1	8	15	1		
Visit window ^a			±3 days	±3 days	±4 days	±3 days	±3 days	±4 days		
Informed consent										
Informed consent/ assent: study procedures ^b	X									5.1
Study procedures										
Physical exam (full)	X									8.2.1
Targeted physical exam		X	X	X	X	X	X	X	X	8.2.1
Vital signs (including peripheral oxygen saturation)	X	X	X	X	X	X	X	X	X	8.2.3
Weight		X			X			X		8.2.1
Height		X			X			X		8.2.1
Tanner staging		X	To be measured at visits where tumor efficacy assessments are made (see Section 8.1) until progression							8.2.4
ECG ^c (single)	X	As clinically indicated								8.2.5
Concomitant medications (including vaccines)	X	X	X	X	X	X	X	X	X	6.4
Demography, including baseline characteristics and tobacco use ^d	X									
Eligibility criteria	X									5.1, 5.2

	Screening	Cycle 1 (28 days)			Cycle 2 (28 days)			Cycle 3 to progression (each cycle is 28 days)	End of Treatment visit	For details, see Section
Day of cycle	-28 to -1	1	8	15	1	8	15	1		
Visit window ^a			±3 days	±3 days	±4 days	±3 days	±3 days	±4 days		
Laboratory assessments										
Clinical chemistry ^c	X	X ^f		X	X		X	X	X	Table 19
Hematology ^c	X	X ^f		X	X		X	X	X	Table 20
Coagulation		X ^f								Table 20
TSH ^g , (if abnormal free T4 ^h ±free T3)	X	X			X			X	X	Table 19
Urinalysis	X	X		X	X		X	X	X	Table 21
Hepatitis B and C and HIV	X									8.2.1
Pregnancy test ⁱ	X	X			X			X	X	8.2.1
Durvalumab PK sample (serum)		X ^{j,k} Pre- and post-infusion of Durva	X	X	X ^{j,k} Pre- ^l and post-infusion of Durva			X ^{j,k} Pre- and post-infusion of Durva ^l in C4, C6, C8, C10, and C12		8.5
Tremelimumab PK sample (serum)					X ^{j,k} Pre- and post-infusion of Treme	X	X	X Pre- and post-infusion of Treme in C3, C4, and C5 ^{j,k} Random sample in C8 ^m	X ^t	8.5
Durvalumab immunogenicity assessment ADA (serum)		X ^j Pre-infusion of Durva only						C6 ^j Pre-infusion of Durva only		8.5
Tremelimumab immunogenicity assessment ADA (serum)					X ^j Pre-infusion of Treme only			C5 ^j and C8 ^m Pre-infusion of Treme only		8.5

	Screening	Cycle 1 (28 days)			Cycle 2 (28 days)			Cycle 3 to progression (each cycle is 28 days)	End of Treatment visit	For details, see Section
Day of cycle	-28 to -1	1	8	15	1	8	15	1		
Visit window ^a			±3 days	±3 days	±4 days	±3 days	±3 days	±4 days		
Monitoring										
Performance Score (Lansky or Karnofsky) ^a	X	X	X	X	X	X	X	X	X	8.2.7
AE/SAE assessment ^o	X	X	X	X	X	X	X	X	X	8.3
IP administration										
Durvalumab infusion ^{fP}		X			X			X		6.1.1 6.1.2
Tremelimumab infusion ^{fP}					X			C3, C4 and C5 only		6.1.1 6.1.2
Other assessments and assays										
CCI										

	Screening	Cycle 1 (28 days)			Cycle 2 (28 days)			Cycle 3 to progression (each cycle is 28 days)	End of Treatment visit	For details, see Section
Day of cycle	-28 to -1	1	8	15	1	8	15	1		
Visit window ^a			±3 days	±3 days	±4 days	±3 days	±3 days	±4 days		
Efficacy evaluation										
Radiological efficacy assessments ^a	Days -21 to -1	On-study tumor assessments occur every 8 weeks ± 1 week (always relative to the date of first dose), until radiological progression plus an additional regularly scheduled follow-up scan. For patients who achieve an objective response (CR, PR) or stable disease, and for whom the response is still evident at 12 months, subsequent tumor assessments are to occur every 16 weeks. Unscheduled assessments can be performed at any time during the study, as clinically indicated, based on signs and symptoms								8.1

Note: All assessments on treatment days are to be performed prior to infusion, unless otherwise indicated.

Note: Patients who restart combination therapy (having subsequently progressed on durvalumab monotherapy following the completion of 4 months of combination therapy) should complete the same assessments starting from the Cycle 2 Day 1 of the dose-finding phase, with the exception of the PK, ADA, blood for CCI analysis, and tumor biopsies.

^a Visit windows are relative to the first day of each cycle.

^b Written informed consent/assent and any locally required privacy act document authorization must be obtained prior to performing any protocol-specific procedures, including screening/baseline evaluations. If laboratory or imaging procedures were performed for alternate reasons prior to signing consent, these can be used for screening purposes with consent of the patient's parent(s)/legally authorized representative(s). However, all screening laboratory assessments must have been obtained within 28 days of Cycle 1 Day 1 and imaging/staging examination results must have been obtained within 21 days of Cycle 1 Day 1. The unique enrollment code will be obtained after ICF signature. Dose-finding phase will be manually supplied.

^c Any clinically significant abnormalities detected require a confirmatory ECG result.

^d Tobacco use will be collected at the Investigator's discretion.

^e Serum or plasma clinical chemistry (including LFT monitoring) and hematology may be performed more frequently if clinically indicated.

^f Results for LFTs, electrolytes, full blood count, urea, and creatinine must be available before commencing an infusion (within 3 days) and reviewed by the treating physician or Investigator prior to dosing. If screening clinical chemistry and hematology assessments are performed within 3 days prior to Day 1 (first infusion day), they do not need to be repeated at Day 1. For coagulation parameters, activated partial thromboplastin time and international normalized ratio are to be assessed at baseline on Day 1 (unless performed within 3 days prior to Day 1).

^g If TSH is measured within 14 days prior to Day 1 (first infusion day), it does not need to be repeated at Day 1. TSH to be measured every 4 weeks from baseline.

^h Free T4 ± free T3 will only be measured if TSH is abnormal or if there is clinical suspicion of an AE related to the endocrine system.

ⁱ For females of childbearing potential only. A urine or serum pregnancy test is acceptable. Females of childbearing potential are required to have a pregnancy test within 7 days prior to the first dose of IP and then every 4 weeks. Pregnancy test may occur on Day 1, but results must be available and reviewed by the treating physician or Investigator prior to commencing an infusion.

^j Predose within 60 minutes of start of the 1st infusion.

^k Within 10 minutes of the end of the 2nd infusion.

^l During the combination treatment period, predose samples for durvalumab PK samples should ideally be taken in the window after tremelimumab has been infused and before durvalumab is infused, within 60 minutes of start of infusion. However, sampling prior to tremelimumab infusion is also acceptable, if considered necessary for logistical/operational reasons.

^m The C8 follow-up tremelimumab PK and ADA sample will be taken 3 months (±1 week) after the last dose of this IP (meets requirement in Table 3).

ⁿ Karnofsky scale to be used for patients ≥16 years of age; Lansky scale to be used for patients ≥1 and <16 years of age.

- ° For AEs/SAEs reported during screening, additional information such as medical history and concomitant medications may be needed.
- P During the combination portion of treatment, tremelimumab will be administered first; the durvalumab infusion will start approximately 1 hour after the end of the tremelimumab infusion. See Section 6.1.2 (Study Drug Administration).
- q See Section 8.8.1 for details around collection, requirement, and exemption for samples for CCI [REDACTED]
- r CCI [REDACTED]
- s See Section 6.1.4 and Section 8.1 for additional details. Imaging modalities appropriate for the tumor type under consideration should be performed and the corresponding objective criteria used to monitor efficacy: solid tumors (RECIST 1.1 [Appendix E], and INRC for neuroblastoma [Appendix F]). Confirmatory scans will be required.
- t A tremelimumab sample is required for patients at the EoT visit who only received a single dose (cycle) of tremelimumab in combination with durvalumab. Preferably, this sample should be collected approximately 30 days after the final tremelimumab infusion, but can be collected at any time after the final (day 15) tremelimumab PK sample.

ADA Anti-drug antibody; AE Adverse event; C Cycle; CR Complete response; CSF Cerebrospinal fluid; D Day; Durva Durvalumab; ECG Electrocardiogram; FFPE Formalin-fixed paraffin-embedded; HIV Human immunodeficiency virus; ICF Informed consent form; IM Intramuscular; INRC International Neuroblastoma Response Criteria; IP Investigational product; LFT Liver function test; LP Lumbar puncture; mRNA Messenger ribonucleic acid; NA Not applicable; CCI [REDACTED] PK Pharmacokinetics; PR Partial response; qXw Every X weeks; RECIST Response Evaluation Criteria In Solid Tumors; SAE Serious adverse event; CCI [REDACTED] Treme Tremelimumab; T3 Triiodothyronine; T4 Thyroxine; TSH Thyroid-stimulating hormone; W Week.

Table 2 Schedule of activities for durvalumab ± tremelimumab dose-expansion phase

	Screening	Cycle 1 (28 days)			Cycle 2 (28 days)		Cycle 3 to progression (each cycle is 28 days)	End of Treatment visit	For details, see Section
Day of cycle	-28 to -1	1	8	15	1	15	1		
Visit window^a			±3 days	±3 days	±4 days	±3 days	±4 days		
Informed consent									
Informed consent/assent: study procedures ^b	X								5.1
Study procedures									
Physical exam (full)	X								8.2.1
Targeted physical exam		X	X	X	X	X	X	X	8.2.1
Vital signs (including peripheral oxygen saturation)	X	X	X	X	X	X	X	X	8.2.3
Weight		X			X		X		8.2.1
Height		X			X		X		8.2.1
Tanner staging		X	To be measured at visits where tumor efficacy assessments are made (see Section 8.1), until progression						8.2.4
ECG ^c (single)	X	As clinically indicated							8.2.5
Concomitant medications (including vaccines)	X	X	X	X	X	X	X	X	6.4
Demography, including baseline characteristics and tobacco use ^d	X								5.1
Eligibility criteria	X								5.1, 5.2
Laboratory assessments									
Clinical chemistry ^e	X	X ^f		X	X	X	X	X	Table 19
Hematology ^e	X	X ^f		X	X	X	X	X	Table 20
Coagulation		X ^f							Table 20

	Screening	Cycle 1 (28 days)			Cycle 2 (28 days)		Cycle 3 to progression (each cycle is 28 days)	End of Treatment visit	For details, see Section
Day of cycle	-28 to -1	1	8	15	1	15	1		
Visit window ^a			±3 days	±3 days	±4 days	±3 days	±4 days		
TSH ^g , (if abnormal free T4 ^h ± free T3)	X	X			X		X	X	Table 19
Urinalysis	X	X		X	X	X	X	X	Table 21
Hepatitis B and C and HIV	X								8.2.1
Pregnancy test ⁱ	X	X			X		X	X	8.2.1
Durvalumab PK sample (serum)		X ^{j,k} Pre- and post-infusion of Durva	X	X	X ^{j,k} Pre ^l - and post-infusion of Durva		X ^{j,k} Pre- and post-infusion of Durva in C4 ^l , C8, C12		8.5
Tremelimumab PK sample (serum)		X ^{j,k} Pre- and post-infusion of Treme	X	X	X ^{j,k} Pre- and post-infusion of Treme		X C4 Pre- and post-infusion of Treme _{j,k} Random sample in C7 ^m		8.5
Durvalumab immunogenicity assessment ADA (serum)		X ^j Pre-infusion of Durva only ^l					C4 ^j Pre-infusion of Durva only		8.5
Tremelimumab immunogenicity assessment ADA (serum)		X ^j Pre-infusion of Treme only					C4 ^j Pre-infusion of Treme only Random sample in C7 ^m		8.5
Monitoring									
Performance Score (Lansky or Karnofsky) ⁿ	X	X	X	X	X	X	X	X	8.2.7
AE/SAE assessment ^o	X	X	X	X	X	X	X	X	8.3

	Screening	Cycle 1 (28 days)			Cycle 2 (28 days)		Cycle 3 to progression (each cycle is 28 days)	End of Treatment visit	For details, see Section
Day of cycle	-28 to -1	1	8	15	1	15	1		
Visit window ^a			±3 days	±3 days	±4 days	±3 days	±4 days		
IP administration									
Durvalumab infusion ^{f,p}		X			X		X		6.1.1 6.1.2
Tremelimumab infusion ^{f,p}		X			X		C3 and C4 only		6.1.1 6.1.2
Other assessments and assays									
CCI									
Blood sample for vaccine antibody titer measurements (blood) ^g		X	At least 4 weeks after vaccination					X	8.9

CCI

	Screening	Cycle 1 (28 days)			Cycle 2 (28 days)		Cycle 3 to progression (each cycle is 28 days)	End of Treatment visit	For details, see Section
Day of cycle	-28 to -1	1	8	15	1	15	1		
Visit window ^a			±3 days	±3 days	±4 days	±3 days	±4 days		
Efficacy evaluations									
Radiological efficacy assessments ^u	X	On-study efficacy assessments occur every 8 weeks ± 1 week (always relative to the date of first dose), until radiological progression plus an additional regularly scheduled follow-up scan. This schedule MUST be followed regardless of any delays in dosing. For patients who achieve an objective response (CR, PR) or stable disease, and for whom the response is still evident at 12 months, subsequent tumor assessments are to occur every 16 weeks. Unscheduled assessments can be performed at any time during the study, as clinically indicated, based on signs and symptoms							8.1

Note: All assessments on treatment days are to be performed prior to infusion, unless otherwise indicated.

Note: Patients who restart combination therapy (having subsequently progressed on durvalumab monotherapy following the completion of 4 months of combination therapy) should complete the same assessments starting from Cycle 1 Day 1 of the dose-expansion phase, with the exception of PK, ADA, tumor biopsies, blood for CCI analysis, blood for CCI sequencing, and CCI.

^a Visit windows are relative to the first day of each cycle.

^b Written informed consent/assent and any locally required privacy act document authorization must be obtained prior to performing any protocol-specific procedures, including screening/baseline evaluations. If laboratory or imaging procedures were performed for alternate reasons prior to signing consent, these can be used for screening purposes with consent of the patient's parent(s)/legally authorized representative(s). However, all screening laboratory assessments must have been obtained within 28 days of Cycle 1 Day 1 and imaging/staging examination results must have been obtained within 21 days of Cycle 1 Day 1. The unique enrollment code will be obtained after ICF signature, through the IRT/RTSM.

^c Any clinically significant abnormalities detected require a confirmatory ECG result.

^d Tobacco use will be collected at the Investigator's discretion.

^e Serum or plasma clinical chemistry (including LFT monitoring) and hematology may be performed more frequently if clinically indicated.

^f Results for LFTs, electrolytes, full blood count, urea, and creatinine must be available before commencing an infusion (within 3 days) and reviewed by the treating physician or Investigator prior to dosing. If screening clinical chemistry and hematology assessments are performed within 3 days prior to Day 1 (first infusion day), they do not need to be repeated at Day 1. For coagulation parameters, activated partial thromboplastin time and international normalized ratio are to be assessed at baseline on Day 1 (unless performed within 3 days prior to Day 1).

^g If TSH is measured within 14 days prior to Day 1 (first infusion day), it does not need to be repeated at Day 1. TSH to be measured every 4 weeks from baseline.

^h Free T4 ± free T3 will only be measured if TSH is abnormal or if there is clinical suspicion of an AE related to the endocrine system.

ⁱ For females of childbearing potential only. A urine or serum pregnancy test is acceptable. Females of childbearing potential are required to have a pregnancy test within 7 days prior to the first dose of IP and then every 4 weeks. Pregnancy test may occur on Day 1, but results must be available and reviewed by the treating physician or Investigator prior to commencing an infusion.

^j Predose within 60 minutes of start of the 1st infusion.

^k Within 10 minutes of the end of the 2nd infusion.

- ¹ During the combination treatment period, predose samples for durvalumab PK samples should ideally be taken in the window after tremelimumab has been infused and before durvalumab is infused, within 60 minutes of start of infusion. However, sampling prior to tremelimumab infusion is also acceptable, if considered necessary for logistical/operational reasons.
- ^m The C7 follow-up tremelimumab PK and ADA sample will be taken 3 months (± 1 week) after the last dose of this IP (Table 3).
- ⁿ Kamofsky scale to be used for patients ≥ 16 years of age; Lansky scale to be used for patients ≥ 1 and < 16 years of age.
- ^o For AEs/SAEs reported during screening, additional information such as medical history and concomitant medications may be needed.
- ^p During the combination portion of treatment, tremelimumab will be administered first; the durvalumab infusion will start approximately 1 hour after the end of the tremelimumab infusion. See Section 6.1.2 (Study Drug Administration).
- ^q Blood sample for antibody titer measurement will be taken from all patients at C1D1 and from at least 14 patients on durvalumab plus tremelimumab combination therapy. At Cycle 1 Day 1, samples will be collected before tremelimumab infusion. Afterwards, a new sample should be collected at least 4 weeks after a vaccine has been given and end of treatment visit. Upon confirmation that a sufficient number of samples has been successfully analyzed, sites will be informed so that further collection of samples can be discontinued.
- ^r Blood samples for CCI will be collected for at least 10 patients receiving durvalumab plus tremelimumab combination therapy.
- ^s See Section 8.8.1 for details around collection, requirement, and exemption for CCI.
- ^t The following tumor markers will be assessed in this study: alpha-fetoprotein for patients with hepatoblastoma and CCI for patients with germ cell tumors.
- ^u See Section 6.1.4 and Section 8.1 for additional details. Imaging modalities appropriate for the tumor type under consideration should be performed and the corresponding objective criteria used to monitor efficacy: solid tumors (RECIST 1.1 [Appendix E]). Confirmatory scans will be required.

ADA Anti-drug antibody; AE Adverse event; C Cycle; CR Complete response; CSF Cerebrospinal fluid; D day; Durva Durvalumab; ECG Electrocardiogram; FFPE Formalin-fixed paraffin-embedded; HIV Human immunodeficiency virus; ICF Informed consent form; IM Intramuscular; IP Investigational product; Interactive Response Technology (IRT); Randomization and Trial Supply Management (RTSM); LFT Liver function test; LP Lumbar puncture; CCI; NA Not applicable; CCI; PK Pharmacokinetics; PR Partial response; qXw Every X weeks; RECIST Response Evaluation Criteria In Solid Tumors; SAE Serious adverse event; CCI; Tremel tremelimumab; T3 Triiodothyronine; T4 Thyroxine; CCI; TSH Thyroid-stimulating hormone; W Week.

Table 3 Schedule of activities for patients who have discontinued all study treatments (durvalumab monotherapy or durvalumab and tremelimumab combination therapy) in the dose-finding or the dose-expansion phases

	Time since last dose of IP				For details, see Section
	Day (± 3)	Months (± 1 week)			
	30	2	3	4 months and every 2 months thereafter (± 2 weeks)	
Evaluation					
Physical examination (full)	X				8.2.1
Vital signs (temperature, respiratory rate, blood pressure, pulse, and peripheral oxygen saturation)	X	X	X		8.2.3
Weight	X	X	X		8.2.1
Pregnancy test ^a	X	X	X		8.2.1
AE/SAE assessment	X	X	X		8.3
Concomitant medications	X	X	X		6.4
Performance Score (Lansky or Karnofsky) performance status ^b	X				8.2.7
Subsequent anticancer therapy ^c	X	X	X	X	8.1.2
Survival status ^d	X	X	X	X	8.1.2
Hematology	X	X	X		Table 20
Clinical chemistry	X	X	X		Table 19
TSH ^e (if abnormal free T4 \pm free T3)	X	X	X		Table 19
Durvalumab PK sample (serum) ^f			X		8.5
Tremelimumab PK sample (serum) ^f			X		8.5
Durvalumab immunogenicity assessment ADA (serum) ^f			X		8.5

	Time since last dose of IP				For details, see Section
	Day (± 3)	Months (± 1 week)			
	30	2	3	4 months and every 2 months thereafter (± 2 weeks)	
Evaluation					
Tremelimumab immunogenicity assessment ADA (serum) ^f			X		8.5
Radiological efficacy assessments ^g	Efficacy assessments occur every 8 weeks (or every 16 weeks for patients who achieve an objective response [CR, PR] or stable disease and for whom the response is still evident at 12 months) ± 1 week relative to the date of first dose, until radiological progression plus an additional regularly scheduled follow-up scan or death (whichever comes first). Additional scans to be completed per standard practice post-progression				7.1

Note: Patients who permanently discontinue drug for reasons other than objective PD should continue to have objective response assessments performed every 8 weeks ± 1 week (when clinically indicated) thereafter until PD plus an additional follow-up assessment or death (whichever comes first). For patients who achieve an objective response (CR, PR) or stable disease and for whom the response is still evident at 12 months, subsequent tumor assessments are to occur every 16 weeks. If a patient is discontinued for PD, then the patient should have 1 additional follow-up assessment performed preferably at the next (and no later than the next) scheduled imaging visit, and no less than 4 weeks after the prior assessment of PD.

^a For females of childbearing potential only. A urine or serum pregnancy test is acceptable.

^b Karnofsky scale to be used for patients ≥ 16 years of age; Lansky scale to be used for patients ≥ 1 and < 16 years of age.

^c Details of any treatment **for the malignancy under study** (including surgery) post the last dose of IP must be recorded in the CRF. At minimum, collect the start date and description of the subsequent anticancer therapy.

^d Patients/parents/legally authorized representatives may be contacted in the week following data cut offs to confirm survival status. Details of any treatment for **the malignancy under study** (including surgery) post the last dose of IP must be recorded in the CRF.

^e Free T4 \pm free T3 will only be measured if TSH is abnormal or if there is clinical suspicion of an AE related to the endocrine system.

^f PK and immunogenicity samples for durvalumab and tremelimumab are collected 90 days (3 months) (± 7 days) after the last dose of that IP (eg, if the last dose of tremelimumab is at C4D1 [12 weeks], then the follow-up samples for tremelimumab PK/ADA will be taken 90 days ± 7 days after that date, so equivalent to C7D1 [24 weeks] of durvalumab monotherapy; if the last dose of durvalumab is, for example, at C8D1, then the follow-up samples for durvalumab PK/ADA will be taken 90 days ± 7 days after that date.

^g See Section 7.1 for additional details. Imaging modalities appropriate for the tumor type under consideration should be performed and the corresponding objective criteria used to monitor efficacy.

ADA Anti-drug antibody; AE Adverse event; CR Complete response; CRF Case report form; IP Investigational product; NA Not applicable; PD progression of disease; PK Pharmacokinetics; PR Partial response; SAE serious adverse event; T3 Triiodothyronine; T4 Thyroxine; TSH Thyroid-stimulating hormone.

Table 4 Schedule of activities for patients receiving ongoing treatment beyond final data cutoff (DCO)

IP Administration	
Durvalumab administration	Every 28 days until disease progression (or meeting criteria for treatment discontinuation)
Laboratory assessments	
Clinical chemistry	Standard of care, per local clinical practice
Hematology	Standard of care, per local clinical practice
TSH	Standard of care, per local clinical practice
Required Monitoring and Reporting	
SAE reporting	Any time during study treatment and up until 90 days after the last durvalumab infusion. If an event occurs after the 90-day period and is considered to be due to a late onset toxicity to study treatment, it should be reported as a SAE.
AESI reporting	Any time during study treatment and up until 90 days after the last durvalumab infusion.. If an event occurs after the 90-day period and is considered to be due to a late immune-related toxicity to study treatment, it should be reported as an AESI.
Pregnancy testing	For females of childbearing potential: Monthly while on study treatment and then monthly x 3 following the completion of study treatment.
Pregnancy reporting	Any time during study treatment
Overdose reporting	Any time during study treatment
Efficacy evaluation	

Radiological efficacy assessments	Imaging schedule as standard of care, per local clinical practice
-----------------------------------	---

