3. Four tremelimumab PK samples (taken predose and end-of -infusion on Day 1 and on Day 8 and Day 15) will be obtained and
4. One sample will be taken on Day 1 prior to dosing of tremelimumab to determine CCI.

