6.1.2 Study Drug Administration

During Cycles 1 and 2 of the dose-finding phase, durvalumab is infused over 120 minutes (2 hours). Starting with Cycle 3, if tolerated, the durvalumab infusion time may be reduced to 60 minutes (1 hour). Tremelimumab infusions will be administered over 60 minutes (1 hour) during all treatment cycles.

- During the dose-expansion phase, all durvalumab infusions will be administered over 60 minutes (1 hour)

On days when both durvalumab and tremelimumab are scheduled (Cycles 2 to 5 in dose-finding phase and Cycles 1 to 4 in dose-expansion phase), the tremelimumab infusion is to be administered *first* followed by a 1-hour interval (maximum 2 hours) before the start of the durvalumab infusion.

- Refer to Section 8.2.3 (Vital signs) for details on required vital signs and observation periods

Both durvalumab and tremelimumab infusions are to be administered using a 0.2 or 0.22 µm low-protein binding in-line filter.

No other drugs are to be infused through the same line or port while study infusions are being administered.

The IV tubing is flushed with a volume of saline equal to the priming volume of the administration set used after the contents of the IV bag or IV syringe are fully administered, according to institutional policy to ensure the full dose is administered.

The study infusion may be interrupted for an infusion reaction and when permitted, is restarted at a slower (ie, 50%) infusion rate. In instances where the total dose cannot be completed using an 8 hour hang time, a new infusion bag must be prepared to complete the study infusion.

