8.5 Pharmacokinetics and anti-drug antibodies

8.5.1 Collection of pharmacokinetic samples and determination of drug concentration

Blood samples will be taken at the time points presented in the SoA (Table 1 and Table 2 for dose-finding and dose-expansion, respectively). It is essential that the actual time and date of collection of each blood sample (whether collected as per protocol or not) will be recorded in the CRF. If a patient is receiving durvalumab + tremelimumab combination therapy, because tremelimumab is infused before durvalumab the following principles will be followed when these samples are scheduled:

- Predose samples for tremelimumab PK will be taken before tremelimumab is infused. Predose samples for durvalumab PK will be taken before durvalumab is infused. During the combination period, predose samples for durvalumab PK should ideally be taken in the interval following tremelimumab administration and before durvalumab is infused. However, sampling prior to tremelimumab infusion is also acceptable, if considered necessary for logistical/operational reasons.
- End of infusion sample for tremelimumab PK will be taken after tremelimumab is infused.
- End of infusion sample for durvalumab PK will be taken after durvalumab is infused.

End of infusion PK samples should be taken within 10 minutes of the completion of IP infusion.

- In the dose-finding phase only, an end of treatment tremelimumab sample is required for patients at the EoT visit who have received only a single dose (cycle) of tremelimumab in combination with durvalumab (i.e treatment discontinuation after cycle 2). Preferably, this sample should be collected approximately 30 days after the final tremelimumab infusion, but can be collected at any time beyond the final (day 15) tremelimumab PK sample collection.

Samples will be collected, labeled, stored, and shipped as detailed in the Laboratory Manual. Samples for determination of durvalumab and tremelimumab concentration in serum will be analyzed by a designated third party on behalf of AstraZeneca.

Full details of the analytical method used will be described in a separate Bioanalytical Validation Report.

8.5.2 Collection of samples to measure for the presence of ADAs and ADA-neutralizing antibodies

The presence of ADA will be assessed in serum samples taken according to the SoAs ([Table 1](#) and [Table 2](#) for dose-finding and dose-expansion, respectively).

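### Footnote k in Tables 1 and 2 times the post-infusion tremelimumab PK sample to the end of the durvalumab infusion, contradicting Section 8.5.1; followed literally, the sample is about 1 to 4 hours late

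*Protocol*

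**What the plan says.** In Table 1 (dose-finding) and Table 2 (dose-expansion) of protocol Section 1.1, the tremelimumab PK cells read "Pre- and post-infusion of Treme" and carry footnotes j and k. Footnote k is the same in both tables: "Within 10 minutes of the end of the 2nd infusion".

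Footnote p fixes the order on combination days: "tremelimumab will be administered first; the durvalumab infusion will start approximately 1 hour after the end of the tremelimumab infusion". Section 6.1.2 gives the same order, with tremelimumab "followed by a 1-hour interval (maximum 2 hours) before the start of the durvalumab infusion". The second infusion is therefore durvalumab.

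Section 8.5.1 gives a different time for the same sample: "End of infusion sample for tremelimumab PK will be taken after tremelimumab is infused". Its window is: "End of infusion PK samples should be taken within 10 minutes of the completion of IP infusion". Section 4.1.1 agrees with 8.5.1 in describing Cycle 2 of dose-finding: "Four tremelimumab PK samples (taken predose and end-of -infusion on Day 1 and on Day 8 and Day 15) will be obtained".

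Footnote l adjusts the shared timing notes for the durvalumab predose sample on combination days. No footnote does so for the tremelimumab post-infusion sample.

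**The concern.** The schedule tables are what sites work from on the day, and here a footnote gives a different instruction from the section that governs PK sampling. A site that follows the footnote draws the tremelimumab sample after the durvalumab infusion has finished.

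Cmax is among the PK parameters named in the dose-finding primary endpoint (protocol Section 3; SAP Sections 1.1.1 and 3.4.1). Protocol Section 9.4.3.2 derives Cmax and time to Cmax for both drugs by non-compartmental methods, and SAP Section 4.2.4.1 summarises them. In dose-finding Cycle 2 the only other post-dose tremelimumab samples in the cycle are on Days 8 and 15, so nothing else in the schedule can supply a missed end-of-infusion value.

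SAP Section 4.2.4.1 also summarises concentrations by planned time point. If some sites follow the footnote and others follow Section 8.5.1, one nominal time point would hold samples taken hours apart.

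**Working it through.** The plan states no figure to reproduce. The check is how far apart the two instructions fall, and what that could do to the PK parameters.

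**Inputs**
- Gap between infusions: 1 h, maximum 2 h (Section 6.1.2). In dose-expansion from Cycle 2 it may be waived, so that durvalumab follows at once (Section 8.2.3).
- Durvalumab infusion: 2 h in dose-finding Cycles 1 and 2; from Cycle 3 it may be cut to 1 h if tolerated; 1 h throughout expansion (Section 6.1.2).
- Tremelimumab infusion: 1 h in all cycles (Section 6.1.2).
- Tremelimumab post-infusion samples: dose-finding Cycles 2 to 5 (Table 1); expansion Cycles 1, 2 and 4 (Table 2).

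**Step 1: the lag.** Lag from end of tremelimumab to end of durvalumab = gap + durvalumab infusion time.

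| Visit | Sum | Lag |
|---|---|---|
| Dose-finding Cycle 2 | 1 + 2 to 2 + 2 | 3-4 h |
| Dose-finding Cycles 3-5, durvalumab shortened | 1 + 1 to 2 + 1 | 2-3 h |
| Dose-finding Cycles 3-5, not shortened | 1 + 2 to 2 + 2 | 3-4 h |
| Expansion Cycle 1 | 1 + 1 to 2 + 1 | 2-3 h |
| Expansion Cycles 2 and 4, gap kept | 1 + 1 to 2 + 1 | 2-3 h |
| Expansion Cycles 2 and 4, gap waived | 0 + 1 | 1 h |

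The draw may follow up to 10 minutes later. Section 8.5.1 allows 10 minutes (0.17 h) after tremelimumab ends. Even at the start of the footnote's window, the draw is outside that limit by 1 - 0.17 = 0.83 h at least and 4 - 0.17 = 3.83 h at most.

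**Step 2: time to Cmax.** With a 1 h infusion, an end-of-infusion sample falls about 1 h after the infusion starts. Under the footnote in dose-finding Cycle 2 it falls 1 + 3 = 4 h to 1 + 4 = 5 h after. Observed time to Cmax moves by the whole lag, whatever the half-life.

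**Step 3: Cmax.** The documents give no tremelimumab half-life, so this step is an assumption shown over a range. With exponential decline after the infusion, fall = 1 - 2^(-lag / half-life).

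| Assumed early half-life | 1 h late | 2 h late | 3 h late | 4 h late |
|---|---|---|---|---|
| 0.5 day | 5.61% | 10.91% | 15.91% | 20.63% |
| 1 day | 2.85% | 5.61% | 8.30% | 10.91% |
| 3 days | 0.96% | 1.91% | 2.85% | 3.78% |
| 7 days | 0.41% | 0.82% | 1.23% | 1.64% |
| 21 days | 0.14% | 0.27% | 0.41% | 0.55% |

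The fall is under 4% in every case unless the early half-life is below 3 days.

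**Step 4: AUC0-28.** Sections 4.1.1 and 4.3.1.1 define adequate exposure on AUC0-28. The lag covers at most 4 h of 28 x 24 = 672 h, or 0.6% of the time window (a share of time, not of area). Section 9.4.3.2 uses actual sampling times, so a late sample enters the calculation where it belongs.

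**Step 5: durvalumab-only days.** Footnote k also sits on durvalumab samples in dose-finding Cycles 1, 6, 8, 10 and 12 and in expansion Cycles 8 and 12. Only one infusion is given on those days, so the footnote has no literal meaning there. It works as written only for durvalumab on combination days.

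**The case against.** The strongest reply is that the right instruction is already in the protocol. The cell that carries the footnote names tremelimumab as the infusion concerned, its row refers the reader to Section 8.5, and Sections 8.5.1 and 4.1.1 both describe an end-of-infusion sample. Section 8.5.1 also points to a Laboratory Manual that is not among the documents. A site that reads all of this may well sample at the right time. On durvalumab-only days the single infusion is the obvious reference.

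This stands as a limit on the consequence. A reader might infer that tremelimumab samples have in fact been drawn late, but the documents do not show which instruction sites follow. It does not remove the contradiction: a footnote is there to specify its cell, this one specifies a different time, and nothing in either table overrides it.

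A reader might also infer that the dose-finding decision or the primary PK objective is compromised. The documents do not support that. Cmax is one listed parameter and is summarised descriptively, while adequacy of exposure is judged on AUC0-28. Sample times are recorded (Section 8.5.1) and used (Section 9.4.3.2), and a population PK model is planned (Section 9.4.3.1), so a late sample with a correct time remains usable.

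Two smaller cautions also hold. The delay is not several hours at every visit, because it can be about 1 h in expansion from Cycle 2. And Section 8.5.1 asks for an end-of-infusion sample, not in terms for a peak; treating it as the source of Cmax is a fair inference from the parameter list.

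**Conclusion.** This is an internal inconsistency of minor weight. Footnote k and Section 8.5.1 set incompatible times for the post-infusion tremelimumab sample in both schedules, and they must be reconciled. Sections 4.1.1 and 8.5.1 agree with each other and with the cell text, so the footnote is the element out of line.

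If the footnote is followed, the sample is about 1 to 4 h late depending on phase and cycle, time to Cmax is shifted by that amount, and Cmax is understated. The understatement is probably modest, but that rests on an assumed half-life. Mixed practice across sites would blur the summaries by nominal time point. The AUC0-28 adequacy decision is little affected, provided that actual times are recorded correctly.

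**What to change.** Reword footnote k in Tables 1 and 2 to: *within 10 minutes of the end of the infusion of the drug being measured*. This matches Section 8.5.1, leaves the durvalumab timing on combination days unchanged, and gives the footnote a meaning on durvalumab-only days.

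For samples already drawn, compare each recorded tremelimumab sample time with the end of the tremelimumab infusion (assuming infusion end times are held in the dosing records). Identify samples outside the 10-minute window before reporting Cmax and time to Cmax, and state how many there are.

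The cost is one footnote in two tables and one data check. No sample, visit or blood volume is added.
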